4. STUDY DESIGN

4.1. Primary and Secondary Outcomes

According to the aim and objectives of this study, safety and efficacy of Polyoxidonium®, lyophilizate for solution for injections and topical application, 6 mg (NPO Petrovax Pharm LLC, Russia) will be evaluated in hospitalized patients with coronavirus disease (COVID-19).

Efficacy outcomes

Primary efficacy outcome

Subject clinical status using the WHO 7-point ordinal scale on day 15 as compared to baseline.

1. Not hospitalized, no limitations on activities.
2. Not hospitalized, limitation on activities.
3. Hospitalized, not requiring supplemental oxygen.
4. Hospitalized, requiring supplemental oxygen.
5. Hospitalized, on non-invasive ventilation or high flow oxygen devices.
6. Hospitalized, on invasive mechanical ventilation or ECMO.
7. Death.

Secondary efficacy outcomes

Clinical severity assessed by scales

1. Subject clinical status using the WHO 7-point ordinal scale

- Time to improvement of each parameter of the primary scale from admission.

- Subject clinical status at days 3, 5, 8, 11, and 29.
 - Average change in the clinical status at days 3, 5, 8, 11, 15, and 29 as compared to baseline.
2. *The NEWS Score (National Early Warning Score) describes the vital signs (pulse rate, breathing rate, temperature, blood pressure etc.) and its deviation from the reference ranges):* is evaluated daily and on day 15.
- The time to discharge or to a NEWS of ≤ 2 and maintained for 24 hours, whichever occurs first.
 - Change from baseline to days 3, 5, 8, 11, 15, and 29 in NEWS.
3. *Oxygenation, including mechanical ventilation:*
- Change (day by day) in the need for oxygenation in the first 28 days (up to day 29).
4. *Hospitalization*
- Duration of hospitalization (days).
5. *Mortality (date, cause)*
- 28-day mortality.
6. *SOFA scale (evaluation of organ failure associated with sepsis):* is evaluated daily and on day 15.
- Change from baseline to days 3, 5, 8, 11, 15, and 29 in SOFA.

Safety outcomes

Safety outcomes

- Cumulative incidence of serious adverse events/reactions (SAEs, SARs)
- Cumulative incidence of adverse events/reaction (AEs, ARs)
- Permanent or temporary discontinuation of infusions/injections (by any cause)
- Clinically significant changes in the levels of leukocytes, haemoglobin, platelets, creatinine, glucose, total bilirubin, ALT, AST, CRP, and other parameters.

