6.3.8. Collection of efficacy data

The efficacy data (the need for oxygenation, the need for mechanical ventilation, continued hospitalization) will be collected daily during the study to assess the effectiveness of therapy during hospitalization. The selected scales are recommended for efficacy assessment by WHO².

The patient status will also be assessed using the following questionnaires/scales in accordance with the description of the study periods and the schedule of the study procedures.

Examples of the scales used in the study

¹ Temporary guidelines. Prevention, diagnosis, and treatment of the novel coronavirus infection (2019-nCoV). Version 2 (02/03/2020). Electronic source with free access: <https://static-i.rosminzdrav.ru/system/attachments/attaches/000/049/329/original/%D0%92%D1%80%D0%B5%D0%BC%D0%B5%D0%BD%D0%BD%D1%8B%D0%B5%D0%9C%D0%A0%2019-nCov%2003.02.2020%28%D0%B2%D0%B5%D1%80%D1%81%D0%B8%D1%8F%2029%20final.pdf?1580748451>. Access date: March 16, 2020.

² MASTER PROTOCOL. A Multi-centre, Adaptive, Randomized, Double-Blind, Placebo-Controlled Clinical Trial of the Safety and Efficacy of Investigational Therapeutics for the Treatment of COVID-19 in Hospitalized Patients. Electronic source with free access: <https://www.who.int/blueprint/priority-diseases/key-action/multicenter-adaptive-RCT-of-investigational-therapeutics-for-COVID-19.pdf>. Access date: March 13, 2020

Measures of clinical support

The following measures of clinical support will be evaluated on each day of hospitalization up to day 17:

- Hospitalization
- Oxygen requirement
- Non-invasive mechanical ventilation (via mask)
- Mechanical ventilator requirement (via endotracheal tube or tracheostomy tube)
- ECMO requirement

7-point ordinal scale

Recommended by WHO as the primary endpoint for evaluating the efficacy of coronavirus infection therapy¹.

The 7-point ordinal scale is an assessment of the clinical status at the first assessment of a given study day. Each day, the worse score for the previous day will be recorded. For example, on day 3, day 2 score is obtained and recorded as day 2. The scale is as follows:

1. Not hospitalized, no limitations on activities.
2. Not hospitalized, limitation on activities.
3. Hospitalized, not requiring supplemental oxygen.
4. Hospitalized, requiring supplemental oxygen.
5. Hospitalized, on non-invasive ventilation or high flow oxygen devices.
6. Hospitalized, on invasive mechanical ventilation or ECMO.
7. Death.

NEWS Score

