9.7.2.2. Analysis of the secondary efficacy endpoints

The interval (quantitative) data will be described with arithmetic mean, standard deviation, median, lower quartile (25%) and higher quartile (75%), minimum, maximum, coefficient of variation, and 95% confidence interval for the mean. The categorical (qualitative) data will be described with incidences, percentage, or proportions, and 95% confidence interval for percentage or proportions.

The time to event data will be processed via survival analysis with the use of Kaplan-Meier curves and 95% confidence intervals.

The following standard parametric tests are planned for comparison of quantitative data with normal distribution: Student t-test for dependent/independent samples, analysis of variance (ANOVA) for repeated measurements.

The following standard non-parametric tests are planned for comparison of quantitative data with distribution other than normal: Mann-Whitney U-test, Wilcoxon T-test, Friedman test.

Shapiro-Wilk test will be used to test normality of the distribution.

The incidences will be compared between the treatment groups with Pearson's χ^2 -test or Fischer's exact test.

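### The secondary endpoint of average change on the 7-point scale weights a death by baseline category, least in the sickest patients, so a ventilated patient's death is cancelled by one mild patient's discharge

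*Combined protocol and SAP*

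**What the plan says.** The combined protocol and SAP defines the primary outcome in section 4.1 as "Subject clinical status using the WHO 7-point ordinal scale on day 15 as compared to baseline". Lower codes are better. The categories that matter here are "1. Not hospitalized, no limitations on activities", "2. Not hospitalized, limitation on activities", "3. Hospitalized, not requiring supplemental oxygen" and "6. Hospitalized, on invasive mechanical ventilation or ECMO", with death coded 7.

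The third item under the first secondary outcome is "Average change in the clinical status at days 3, 5, 8, 11, 15, and 29 as compared to baseline". The Synopsis and section 7.1 repeat it.

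Section 9.7.2.2 gives generic methods for secondary endpoints:
- Quantitative data are summarised by mean, SD, median, quartiles, coefficient of variation and a confidence interval for the mean.
- Categorical data are summarised by percentages with confidence intervals.
- Quantitative comparisons use the t-test or repeated-measures ANOVA if normality holds by Shapiro-Wilk, and otherwise Mann-Whitney, Wilcoxon or Friedman tests.

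The section does not say which route the WHO scale takes, names no ordinal method, and has no rule for deaths in the average. Section 9.4 rules out substitution of missing data and does not say that code 7 is kept at days after death.

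Section 5.1 admits both patients who need mechanical ventilation and mild-moderate patients without oxygen. Section 4.2 puts them all in one treated group with no comparator.

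**The concern.** An ordinal scale gives an order and no distances. Subtracting codes treats every step as equal, so the weight of a death depends on where the patient started: the sicker the patient at entry, the less the death counts. A move from ventilation to death scores the same as a move from no oxygen to supplemental oxygen.

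Because ventilated and mild patients share one group, discharges of mild patients can outweigh deaths of ventilated ones, and the average can be read as benefit in a cohort with substantial mortality. There is no control arm to show what average change would have occurred without the drug. Section 4.2 also names change in clinical status as a basis for judging efficacy, so this figure is likely to be cited as efficacy evidence at six days.

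**Working it through.** **Inputs.** Category codes and the endpoint come from section 4.1, eligibility of ventilated and mild patients from section 5.1, the single group from section 4.2, and at least 50 patients from the Synopsis. The Synopsis gives no derivation for 50, so there is no plan figure to reproduce. *Assumptions, because the documents give no values:* baseline mix, death rate and two-sided testing at 0.05.

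**Step 1: points per death.** Change = follow-up code - baseline code.
- From 3: 7 - 3 = +4
- From 4: 7 - 4 = +3
- From 5: 7 - 5 = +2
- From 6: 7 - 6 = +1

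A mild discharge is 2 - 3 = -1 or 1 - 3 = -2. One ventilated death plus one 3-to-2 discharge averages (1 - 1)/2 = 0. With a 3-to-1 discharge the pair averages (1 - 2)/2 = -0.5.

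**Step 2: mortality at which the mean is zero.** With d points added per death and g points gained per discharge, break-even mortality = g/(g + d).
- Deaths from 6: 1/(1 + 1) = 50% against 3-to-2 discharges; 2/(2 + 1) = 67% against 3-to-1.
- Deaths from 3: 1/(1 + 4) = 20% and 2/(2 + 4) = 33%.

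**Step 3: cohorts of 50.** V ventilated patients all die and the other 50 - V are mild and discharged. Mean = [V - g(50 - V)]/50.

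| Mortality | All others 3-to-1 (g = 2) | All others 3-to-2 (g = 1) |
|---|---|---|
| 20% (V = 10) | (10 - 80)/50 = -1.40 | (10 - 40)/50 = -0.60 |
| 30% (V = 15) | (15 - 70)/50 = -1.10 | (15 - 35)/50 = -0.40 |
| 50% (V = 25) | (25 - 50)/50 = -0.50 | (25 - 25)/50 = 0.00 |

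At 20% with 3-to-1 discharges the 95% CI is -1.74 to -1.06. At 30% with 3-to-2 discharges it is -0.66 to -0.14.

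**Step 4: a less extreme mix.** Ten start at 6 and all die (+10). Fifteen start at 4: 3 die (+9) and 12 reach 2 (-24). Twenty-five start at 3: 1 dies (+4), 12 reach 2 (-12) and 12 reach 1 (-24). The sum is -37, so the mean is -37/50 = -0.74 (95% CI -1.21 to -0.27), with 14/50 = 28% mortality.

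**Step 5: same mean, different mortality.** Fifteen ventilated deaths with 35 discharges 3-to-2 give -0.40. No deaths, 30 patients unchanged and 20 discharges 3-to-2 give -20/50 = -0.40 as well.

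**Step 6: tests on two of the cohorts.**

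| Test of change | 20% mortality, 3-to-1 | 30% mortality, 3-to-2 |
|---|---|---|
| Ordinary Wilcoxon signed-rank (plan's non-normal route) | p = 1.8e-9 | p = 0.005 |
| Sign test | p = 2.4e-5 | p = 0.007 |
| Signed-rank, death ranked as worst change | p = 0.06 | p = 0.94 |

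The ordinary signed-rank test ranks the sizes of the code differences, so it inherits the weighting. The sign test uses direction only, so ranking death worst cannot alter it.

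**Step 7: within the severe stratum.** Ten deaths from 6 and 15 patients going 4-to-2 give (10 - 30)/25 = -0.80 (95% CI -1.42 to -0.18) at 40% mortality. Splitting by severity does not by itself cure the average.

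**The case against.** The strongest defence is that the plan does not depend on this figure. It is one item in a secondary list that also contains 28-day mortality and clinical status at days 3, 5, 8, 11 and 29, while day-15 status is the primary outcome. Section 9.7.2.2 also provides percentages with confidence intervals, and section 9.7.2.1 provides a severity split, though only under the primary endpoint. This stands. A reader might infer that deaths vanish from the report or that the primary outcome is averaged too. The documents support neither: only the secondary item specifies an average.

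A reader might also infer that the plan would report a t-test. In the 20% cohort with 3-to-1 discharges that gives p = 1.1e-10. But those data take two values and fail Shapiro-Wilk (p = 6e-12), so the plan's own rule leads to Wilcoxon. The conclusion is the same, but the t-test figure is not a consequence of the plan.

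A third inference is that averaging alone creates the apparent improvement. It does not. In that cohort 40 of 50 patients improve, and even the sign test favours improvement. Much of the effect comes from pooling mild and ventilated patients in one uncontrolled group. Averaging adds the unequal weighting of death.

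Section 9 never assigns this scale to the quantitative route. Using the mean is an inference, though a close one, from an endpoint defined as an average.

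Finally, section 6.3.8 describes the scale as "Recommended by WHO as the primary endpoint for evaluating the efficacy of coronavirus infection therapy". That supports the scale. It says nothing about averaging its codes, which is the only objection here.

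**Conclusion.** The point holds for this secondary summary and no further. By arithmetic on the plan's own codes, the weight of a death runs from +4 down to +1 as baseline worsens. The value of +1 belongs only to patients ventilated at baseline. Where deaths come from category 3, the average turns unfavourable at much lower mortality.

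In the assumed cohorts the mean still indicates improvement at 20% to 30% mortality, and at 50% it is either zero or still favourable. These sizes illustrate what the endpoint can do and do not predict the trial's result, because baseline mix and death rates are assumed. Rank testing as planned does not remove the problem. The change should be made, but the primary outcome and the mortality endpoint are not affected.

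**What to change.** At each listed day, by baseline severity, replace the average change with:
- a cross-table of baseline category by category on that day;
- the percentages improved by at least 1 category, improved by at least 2, unchanged, worsened but alive, and dead, each with an exact 95% CI;
- a stated rule that code 7 is kept at all days after death, so that deaths do not drop out as missing.

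If a mean is kept, label it descriptive and attach no test. If a test is wanted, use a signed-rank test within baseline severity, with death ranked as the worst change whatever the baseline. Do not offer a sign test as an alternative, because it ignores the death rule.

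The cost is SAP wording and one table shell, since all the data are already collected. The downside is that there is no single mean to set beside reports that use one.

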ENROLLMENT CRITERIA	
INCLUSION CRITERIA
 
 1. The patient is taking or have been prescribed Polyoxidonium® in accordance with the approved labelling in combination with COVID-19 therapy recommended by the Ministry of Health of the Russian Federation. 2. Verified diagnosis: COVID-19 . 3. Severity of the disease at hospitalization: 
 – severe disease: requiring mechanical ventilation or oxygen, a SpO₂ ≤ 94% on room air or tachypnoea (respiratory rate ≥ 24 breaths/min) – mild-moderate disease: SpO₂ ≥ 94% and respiratory rate ≤ 24 breaths/min without supplemental oxygen. 4. Patients who signed the informed consent. 5. Understands and agrees to comply with planned study procedures. 6. Age ≥18 years old at the enrolment. 7. Has laboratory-confirmed SARS-CoV-2 infection as determined by PCR, or other commercial or public health assay in any specimen prior to enrolment. 
EXCLUSION CRITERIA
 
 1. Pregnancy and lactation. 2. Pathological conditions that make participation in the study impossible for the patient (as judged by the investigator). 3. Participation in any other clinical study during this study, including participation in a clinical study within 30 days before the informed consent. 4. Increased sensitivity to any component of the investigational product. 5. Acute or chronic renal failure. 
WITHDRAWAL CRITERIA
 
 1. The investigator decided that withdrawal from the study is in the patient's interests. 2. Withdrawal of the informed consent (the patient does not want to continue participation in the study). 3. Serious deviation from the study protocol. 4. Idiosyncrasy to the investigational products that developed during the treatment period. 5. AE/SAE that requires an examination and/or treatment that would affect the study procedures significantly. 6. Patient non-compliance. 7. The patient was enrolled by mistake. 8. The patient receives/needs an additional treatment that could affects result of the study or the patient safety. 9. Other conditions or events that require patient withdrawal, as judged by the study doctor.
INVESTIGATIONA	INVESTIGATIONAL PRODUCT

L

**PRODUCT,
DOSAGE,
TREATMENT
REGIMEN**

Polyoxidonium® (azoximer bromide), lyophilizate for solution for injections and topical application.

DOSAGE

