This score is based on 7 clinical parameters. The NEWS scale is used to evaluate efficacy and is recommended by WHO².

Literature shows that the NEWS score allows discriminating patients at risk of adverse outcomes [Smith et al., 2016].

This should be evaluated at the first assessment of a given study day. These parameters can be obtained from the hospital chart using the last measurement prior to the time of assessment. This is recorded for the day obtained. For example, on Day 3, Day 3 score is obtained and recorded as Day 3.

Physiological parameters	3	2	1	0	1	2	3
Respiration rate	≤8		9–11	12-20		21 -24	≥25
Oxygen saturation	≤91	92-93	94-95	≥96			

¹ WHO R&D Blueprint novel Coronavirus COVID-19 Therapeutic Trial Synopsis. Electronic source with free access: https://www.who.int/blueprint/priority-diseases/key-action/COVID-19_Treatment_Trial_Design_Master_Protocol_synopsis_Final_18022020.pdf. Access date: March 20, 2020.

² MASTER PROTOCOL. A Multi-centre, Adaptive, Randomized, Double-Blind, Placebo-Controlled Clinical Trial of the Safety and Efficacy of Investigational Therapeutics for the Treatment of COVID-19 in Hospitalized Patients. Electronic source with free access: <https://www.who.int/blueprint/priority-diseases/key-action/multicenter-adaptive-RCT-of-investigational-therapeutics-for-COVID-19.pdf>. Access date: March 13, 2020

Physiological parameters	3	2	1	0	1	2	3
Any Supplemental Oxygen		Yes		No			
Temperature	≤35.0		35.1-36.0	36.1-38.0	38.1-39.0	≥39.1	
Systolic BP	≤90	91-100	101-110	111-219			≥220
Heart Rate	≤40		41-50	51-90	91-110	111-130	≥131
Level of Consciousness				A			V, P, or U

Level of consciousness = alert (A), and arousable only to voice (V) or pain (P), and unresponsive (U).

SOFA Score

The SOFA scale is used to evaluate the clinical state and is recommended by WHO. Moreover, the SOFA scale was chosen because it is widely known, simple and applicable to most hospital settings. It was developed by the Sepsis Task Force of the European Society of Critical Medicine.

SOFA Organ Deficiency Assessment (Sepsis-related Organ Failure) is a point scale for assessing multiple organ failure in patients with septic syndrome who are in intensive care. This scale was created to quickly calculate and describe a number of complications in critically ill patients. The scale is intended rather for quick scoring and description of a number of complications than for predicting the outcome.

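### Time to discharge or NEWS ≤2 can be reached without any improvement, because eligibility sets no minimum baseline NEWS

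*Combined protocol and SAP*

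**What the plan says.** Among the secondary efficacy outcomes, the Synopsis and sections 4.1 and 7.1 each list "The time to discharge or to a NEWS of ≤ 2 and maintained for 24 hours, whichever occurs first". The target is an absolute level held for a day; no reduction from the Day 1 value is required.

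The inclusion criteria (Synopsis and section 5.1) admit two severity strata. One is "mild-moderate disease: SpO₂ ≥ 94% and respiratory rate ≤ 24 breaths/min without supplemental oxygen". The other is defined by need for oxygen or ventilation, saturation of 94% or below on room air, or a respiratory rate of 24 or more. Neither stratum, nor any other criterion, refers to NEWS.

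Section 6.3.8 says of NEWS: "This score is based on 7 clinical parameters", and gives the scoring table. Section 6.2 and Table 1 have it scored on Day 1 and then daily.

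Sections 9.1 and 9.7.2.2 plan Kaplan-Meier curves with 95% confidence intervals for time-to-event data. Nothing states how to treat a patient whose NEWS is already 2 or below on Day 1. Section 4.2 places all patients in one group. Section 9.7.2 makes all enrolled patients the main efficacy population.

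**The concern.** A time-to-recovery endpoint should start from patients who have not yet recovered on the measure used. Here a patient can enter in the target state, stay there for a day, and be counted as an early success. The curve then drops steeply after about 24 hours for a reason unrelated to treatment or to the course of illness.

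In a randomized comparison both arms would share this early drop. This study has no comparator, so the absolute median is itself the result, and it moves with whoever happens to be enrolled. The plan recognises a similar hazard for the primary endpoint: section 9.7.2.1 expects different trajectories by baseline severity and calls for analyses by severity. That text covers the primary endpoint only. The subgroup list in section 9.9 is also for the primary outcomes and does not name severity.

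The gap also leaves open a choice that affects the answer. Sections 9.3 and 9.7 allow methods to be replaced or selected after data collection, so whether these patients count could be settled once the data are known.

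**Working it through.** The plan gives no expected median, event rate or baseline NEWS distribution, so there is no figure of its own to reproduce. The check has three steps.

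**Step 1: score the eligibility bands on the plan's own table.** From section 6.3.8: rate 12-20 scores 0, 21-24 scores 2, 25 or more scores 3. Saturation of 96 or more scores 0, 94-95 scores 1, 92-93 scores 2, 91 or less scores 3. Supplemental oxygen scores 2. Temperature, systolic pressure, heart rate and consciousness are set to 0 here.

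| Stratum | Profile | NEWS |
|---|---|---|
| Mild-moderate | rate 12-20, saturation ≥96 | 0 + 0 = 0 |
| Mild-moderate | rate 12-20, saturation 94-95 | 0 + 1 = 1 |
| Mild-moderate | rate 21-24, saturation ≥96 | 2 + 0 = 2 |
| Mild-moderate | rate 21-24, saturation 94-95 | 2 + 1 = 3 |
| Severe | on oxygen, saturation ≥96, rate 12-20 | 2 + 0 + 0 = 2 |
| Severe | room air, saturation 92-93, rate 12-20 | 2 + 0 = 2 |
| Severe | room air, saturation ≥96, rate 24 | 0 + 2 = 2 |
| Severe | on oxygen, saturation 94-95, rate 12-20 | 2 + 1 + 0 = 3 |

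Three of the four mild-moderate bands, and three of the severe profiles shown, are at or below 2. The other items can lift a patient out: temperature 38.1-39.0 adds 1 and 39.1 or more adds 2; heart rate 91-110 adds 1 and 111-130 adds 2.

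**Step 2: date the event.** The score must be held for 24 hours. A patient at 2 or below on Day 1 who does not worsen therefore completes the NEWS route about one day later, with no change in condition.

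**Step 3: illustrate the effect on the median.** Let q be the share starting at 2 or below, all scoring the event at 1 day. Let the rest follow an exponential time with median m. For t ≥ 1 day:

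F(t) = q + (1 − q)(1 − exp(−ln2 · t/m))

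Setting F(t) = 0.5 gives t = −(m/ln2) · ln(0.5/(1 − q)), with a floor of 1 day. Both q and m are assumptions.

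- m = 8, q = 20%: 0.5/0.8 = 0.625; t = 8 × 0.470/0.693 = 5.4 days.
- m = 8, q = 40%: 0.5/0.6 = 0.833; t = 8 × 0.182/0.693 = 2.1 days.
- m = 8, q ≥ 50%: half or more have the event at 1 day, so the median is about 1 day.

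| Assumed m (days) | q = 0 | 10% | 20% | 30% | 40% | ≥50% |
|---|---|---|---|---|---|---|
| 8 | 8.0 | 6.8 | 5.4 | 3.9 | 2.1 | 1.0 |
| 10 | 10.0 | 8.5 | 6.8 | 4.9 | 2.6 | 1.0 |
| 14 | 14.0 | 11.9 | 9.5 | 6.8 | 3.7 | 1.0 |

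In a study of 50, shares of 20%, 40% and 50% are 10, 20 and 25 patients.

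**The case against.** The strongest reply is that the consequence is limited. This is one of many secondary outcomes, no between-arm effect is estimated from it, and any single-arm median depends on case mix. Change in NEWS from baseline and duration of hospitalization are reported separately. Restricting to baseline NEWS above 2 still mixes patients at 3 with much sicker ones, and it departs from the all-enrolled population. All of this is fair. The restriction reduces the case-mix problem without removing it, and the departure is answered by keeping the all-patient curve as supportive. What remains is that starting in the target state differs from starting closer to it: the first kind of event contains no recovery at all.

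A reader might go further and infer that mild-moderate patients as a group have already met the endpoint at baseline, with a time near zero that treatment cannot alter. The documents do not support that:

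- The 24-hour hold puts the earliest NEWS-based event at about one day, so a median of zero does not follow even with half the patients already at 2 or below.
- A patient can worsen within the day and miss the event.
- Rate 21-24 with saturation 94-95 scores 3, and fever or tachycardia can lift others above 2.
- Some severe patients qualify, so the driver is baseline NEWS rather than the number of mild cases.

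**Conclusion.** The point holds as a defect in the definition of one secondary endpoint. As written, it can be satisfied without improvement by many eligible patients in both severity strata, and no rule says how to handle them. That follows directly from the scoring table and the eligibility text.

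Its size cannot be determined from the documents. The medians above show direction and sensitivity only; they rest on an assumed exponential shape, assumed medians of 8 to 14 days and assumed shares at or below 2. It would be wrong to conclude that the median depends mainly on this share, because nothing in the plan shows that 40% or 50% is likely. At an assumed 10% the median of 8 days falls only to 6.8. The primary endpoint is untouched. This is a cheap and worthwhile clarification, to be made before the data are seen.

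**What to change.** Add a short rule to section 9.7.2.2:

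- The main analysis of this endpoint is in patients with Day 1 NEWS above 2.
- The number and percentage with Day 1 NEWS of 2 or below are reported, and these patients are described by time to discharge.
- The Kaplan-Meier curve for all enrolled patients is kept as a supportive analysis.

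No new data or visits are needed: Day 1 NEWS is already collected, and duration of hospitalization is already an outcome. The cost is fewer patients, and so a wider confidence interval, in this one secondary analysis of a study planned for at least 50.

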4.2. Type/design of the study

This study is an open multi-centre observational study evaluating the efficacy and safety of a non-interventional drug.

The design of a non-invasive non-interventional study was chosen to evaluate the efficacy of the drug in routine clinical practice. Since this study will be non-interventional, all procedures will be carried out in strict accordance with the standards of routine clinical practice and meet the non-interventional criteria set by the Good Pharmacovigilance Practice of the Eurasian Economic Union [approved by the decision of the Council of the Eurasian Economic Commission dated 03.11.2016 No. 87].

No	CRITERION	CONTENT
1	Object, MA	Drug products approved for human use; with a valid marketing authorization
2	Rationale for prescription	As judged by the doctor within the routine clinical practice
3	Time of prescription	Prior to inclusion in the study and regardless of the decision to participate
4	Requirements to the prescription	According to the approved therapeutic indications (therapeutic indications, dosage, etc.)

According to the current routine practice, up-to-date and widely accepted

5	Patient management	clinical guidelines and guides According to the protocol, however, the intervention in the routine management of the patient is minimal
6	Randomization, blinding	Not applicable

The clinical efficacy will be assessed by changes in the patient’s clinical status, duration of hospitalization, oxygenation/mechanical ventilation. The clinical examination will include clinical, laboratory, and instrumental investigations according to the current guidelines on treatment of COVID-19 in the Russian Federation. No additional procedures, except for the special scales (non-invasive), will be carried out during the planned non-interventional study.

The overall objective of the study is to evaluate the clinical efficacy of the investigational product in adult patients hospitalized with COVID-19. The primary endpoint is the patient’s clinical status (in a 7-point ordinal school) on day 15 in accordance with the WHO Master Protocol¹.

The study will be conducted in the clinical centre during hospitalization and outpatient visits of patients to the clinical centre, if necessary.

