9.4. Drop-outs, withdrawn patients, and missing data

No missing data will be substituted. The missing/omitted data will not be considered during statistical analysis.

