9.6. Population for analysis

The following populations will be used for analysis:

1. All enrolled patients (Intent-to-treat, ITT).
2. Safety population: Patients who received at least one infusion, according to the prescribed treatment.

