9.7.2. Statistical methods for efficacy analysis

ITT will be the main population for efficacy analysis.

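### Duration of hospitalization has no rule for in-hospital death or an unfinished stay, so on the plain reading an early death counts as a short stay

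*Combined protocol and SAP*

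**What the plan says.** - **Endpoint.** Section 4.1 lists "Duration of hospitalization (days" as a secondary efficacy outcome. The synopsis and section 7.1 repeat it. Nothing follows the unit: no start point, end point, or rule for death or an unfinished stay.
- **Role.** Section 4.2 states: "The clinical efficacy will be assessed by changes in the patient’s clinical status, duration of hospitalization, oxygenation/mechanical ventilation".
- **Population.** Section 9.7.2: "ITT will be the main population for efficacy analysis". Section 9.6 defines that set as "All enrolled patients (Intent-to-treat, ITT"), so patients who die are in it.
- **Summary.** Section 9.7.2.2 offers two routes. One is for quantitative data: "The interval (quantitative) data will be described with arithmetic mean, standard deviation, median" and further descriptive statistics. The other is: "The time to event data will be processed via survival analysis with the use of Kaplan-Meier curves and 95% confidence intervals". Length of stay is assigned to neither, and the second route has no censoring or competing-risk rule.
- **Missing data.** Section 9.4: "No missing data will be substituted". It adds that missing data are left out of the analysis.
- **Death elsewhere.** Death is the worst category of the 7-point primary scale, and 28-day mortality, with date and cause, is a separate secondary outcome (section 4.1). Neither is linked to length of stay.

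**The concern.** Deaths are foreseeable here: section 5.1 admits patients with severe disease, including those on mechanical ventilation. If length of stay is a number of days averaged over everyone enrolled, a stay ended by death on day 5 is a complete observation of 5 days. It reads as better than a survivor's discharge on day 14. A shorter average could then reflect recovery or early death, and the figure alone would not show which.

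The opposite end has the same gap. A patient still in hospital at the last visit has no completed stay. If that value is treated as missing, section 9.4 leaves it out, and the longest stays are the ones lost.

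Section 11.9 requires the report to reach a clear conclusion on efficacy, and section 4.2 counts length of stay among the ways efficacy is judged. The gap can also work against the product: if treatment prevented early deaths, the mean stay could lengthen.

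**Working it through.** **Inputs.** The documents give no expected stay, mortality or timing of death, and the sample size (at least 50) has no calculation behind it. There is therefore no figure of the plan's own to reproduce. All values below are assumptions, used to show direction and range.

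**1. Mean stay with death as the end of stay.** Let m be mortality, S the survivors' mean stay and D the mean day of death.

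Mean stay = (1 − m)·S + m·D, so the change per 10 points of mortality is 0.1·(D − S).

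With S = 14 days:

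| Mortality | D = 5 | D = 8 | D = 14 | D = 22 |
|---|---|---|---|---|
| 0% | 14.0 | 14.0 | 14.0 | 14.0 |
| 10% | 13.1 | 13.4 | 14.0 | 14.8 |
| 20% | 12.2 | 12.8 | 14.0 | 15.6 |
| 30% | 11.3 | 12.2 | 14.0 | 16.4 |
| Change per 10 points | −0.9 | −0.6 | 0 | +0.8 |

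With S = 18 the changes per 10 points are −1.3, −1.0, −0.4 and +0.4 day. The sign depends only on whether deaths come before or after the survivors' mean stay.

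**2. Unfinished stays.** Suppose 5 of 50 patients are still in hospital at day 29 and the other 45 average 14 days. Leaving the 5 out gives 14.0 days. Counting them at 29 days, which is a minimum, gives (45 × 14 + 5 × 29)/50 = 775/50 = 15.5 days. Omission would shorten the mean by at least 1.5 days under these assumptions.

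**3. Kaplan-Meier instead.** In a simulation, survivors' stays followed a gamma distribution with mean 15 days and deaths a gamma distribution with mean day 8, with follow-up cut at day 29. Median days:

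| Mortality | End of stay by any cause | Kaplan-Meier, death censored | Death counted as never discharged |
|---|---|---|---|
| 0% | 14.2 | 14.2 | 14.2 |
| 10% | 13.5 | 14.4 | 15.0 |
| 20% | 12.8 | 14.6 | 16.1 |
| 30% | 12.0 | 14.8 | 17.8 |

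Censoring deaths removes the reversal but barely registers the mortality. The last column is the time by which half of all patients have been discharged alive.

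**4. Days alive and out of hospital to Day 28.** Score in-hospital deaths 0, count stay from Day 1, and assume that all survivors leave by Day 28 with S = 14. The mean is (1 − m)·(28 − 14), which is 14.0, 12.6, 11.2 and 9.8 days at 0, 10, 20 and 30% mortality. D has dropped out, so higher mortality always worsens the result.

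**5. Scale.** With 50 patients and an assumed SD of 5, 8 or 10 days, the 95% half-width for a mean is 1.96·SD/√50 = 1.4, 2.2 or 2.8 days. A 10-point mortality shift moves the mean by less than this. A 30-point shift with deaths at day 5 moves it by 2.7 days, which is comparable.

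**The case against.** The strongest reply is that the plan is silent rather than wrong, and that little depends on this endpoint. Much of that stands.

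- A reader might infer that the plan counts deaths as completed stays. It does not say so. The quantitative summary is the plain reading of a variable given in days, but Kaplan-Meier is also on offer and the assignment is not made.
- A reader might infer that higher mortality always improves this endpoint. It does so only when deaths come earlier than the survivors' mean stay. Ventilated patients are eligible and may die late, which lengthens the mean.
- A reader might infer that section 9.4 drops patients still in hospital. It does not say whether an unfinished stay is missing, censored or counted to the last visit.
- A reader might take section 4.2 to rank length of stay among the chief efficacy measures. It lists three without ranking them, and section 4.1 places this one among the secondary outcomes.
- Section 4.2 describes a single study group, so no between-arm test can be biased. No success criterion is tied to length of stay, and a reader of the report would see 28-day mortality beside it.

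These points limit the consequence but do not close the gap. Each available reading gives a different answer to the same data, the choice is left until after data collection, and Kaplan-Meier with deaths censored still understates harm.

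**Conclusion.** The concern holds as a missing rule. The plan does not say how in-hospital death, or a stay still open at day 29±3, enters duration of hospitalization. On the plain reading, a death before the survivors' typical discharge is scored as a short stay. With an assumed survivor stay of 14 days, the effect runs from −0.9 day per 10 points of mortality (deaths averaging day 5) through nil (day 14) to +0.8 day (day 22). The direction therefore cannot be known in advance. What is at risk is the descriptive estimate and any subgroup or external comparison made with it. The primary endpoint and the mortality endpoint are unaffected. The point should be corrected, in proportion to a secondary outcome in a single-arm study.

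**What to change.** Prespecify one of two analyses for this outcome:

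1. Cumulative incidence of discharge alive, with death as a competing event and patients still in hospital censored at last contact; or
2. Days alive and out of hospital from Day 1 to Day 28, with in-hospital deaths and patients still in hospital scored 0.

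In either case:

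- State the time origin. Section 5.1 allows patients already receiving the drug at enrolment, so Day 1 need not be admission.
- State how readmission and death after discharge are handled. The documents do not mention readmission, and contact after discharge may be by telephone (section 6.2).
- For option 2, state what happens when the last visit falls before Day 28, since the ±3 window allows Day 26.
- Report raw stay only descriptively, among patients discharged alive.

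The cost is mainly wording in sections 4.1, 7.1 and 9.7.2.2, and in the synopsis. Date of death is already part of the mortality outcome, and discharge timing is already needed for the time to discharge or NEWS outcome. The sponsor should confirm that the CRF has an explicit discharge date and a readmission item, because the documents show neither. The downside is slightly more analysis work and a less familiar summary.
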